5.3.2 Drug Concentration Measurements

5.3.2.1 Collection of Samples for Analysis

Blood Samples for Risankizumab Assay

Blood samples for risankizumab assay will be collected at each study visit by venipuncture into appropriately labeled collection tubes. Blood collection will occur after

patient reported outcomes, clinical assessments, ECG, vital signs, and before study drug administration. The time of collection will be recorded to the nearest minute and at the visits specified in [Appendix C](#).

Seven samples will be collected per subject for PK analysis during the treatment and follow-up periods with the potential for one more sample collected in the event of a hypersensitivity reaction.

Blood Samples for Risankizumab Anti-Drug Antibody (ADA) Assay:

Blood samples for risankizumab ADA assay will be collected at each study visit by venipuncture into appropriately labeled collection tubes. Blood collection will occur after questionnaires, clinical assessments, ECG, vital signs, and before study drug administration. The time of collection will be recorded to the nearest minute and at the visits specified in [Appendix C](#).

Seven samples will be collected per subject for ADA analysis during the treatment and follow-up periods with the potential for one more sample collected in the event of a hypersensitivity reaction.

5.3.2.2 Handling/Processing of Samples

Details for the handling and processing of the samples will be provided outside this protocol in the laboratory manual.

5.3.2.3 Disposition of Samples

The frozen plasma samples for risankizumab concentration and risankizumab ADA assays will be packed and shipped from the study site to the Central Laboratory according to instructions in the central laboratory Lab Manual. An inventory of the samples included will accompany the package.

5.3.2.4 Measurement Methods

Plasma concentrations of risankizumab and relative titers of risankizumab ADA will be determined using validated methods under the supervision of the Bioanalysis department at AbbVie. Any additional analytes may be analyzed using non-validated methods.

Plasma samples collected for risankizumab and risankizumab ADA analysis may be used for future assay development or validation activities. Risankizumab ADA samples upon request may be used for the analysis of neutralizing anti-drug antibodies.

5.3.3 Efficacy Variables

The baseline as defined in Study 1311.5 will be used to derive the efficacy endpoints in this study.

5.3.3.1 Primary Endpoint(s)

Not applicable.

5.3.3.2 Secondary Endpoint(s)

- ACR 20 response at all measured time points
- Change in mTSS at Week 24 and 48 as compared to baseline

5.3.3.3 Further Endpoint(s)

Further efficacy endpoints will include, but are not limited to, the following:

- ACR 50 at all measured time points
- ACR 70 at all measured time points
- Change in Tender Joint Count at all measured time points as compared to baseline
- Change in Swollen Joint Count at all measured time points as compared to baseline
- Change in HAQ-DI at all measured time points as compared to baseline
- Change in SF-36 at all measured time points as compared to baseline

- Change in Dactylitis count at all measured time points as compared to baseline
- Change in SPARCC Enthesitis Index at all measured time points as compared to baseline
- Change in mNAPSI at all measured time points as compared to baseline
- Change in PhGA (VAS) at all measured time points as compared to baseline
- Change in Patient's Assessment of PsA Pain Intensity (VAS) at all measured time points as compared to baseline
- Change in PtGA assessments at all measured time points as compared to baseline
- Change in High sensitivity C-Reactive Protein (hsCRP) at all measured time points as compared to baseline
- Minimal disease activity (MDA) at all measured time points
- Change in DAS28-hsCRP at all measured time points as compared to baseline
- PsO endpoints assessed at all measured time points in subjects with a $\geq 3\%$ baseline PsO BSA:
 - PASI 75 and PASI 90 response
 - Change in sPGA clear and almost clear
- EULAR (European League Against Rheumatism) response at all measured time points
- Change in PsARC (Psoriatic Arthritis Response Criteria) at all measured time points as compared to baseline
- Presence of dactylitis (yes/no) at all measured time points
- Change in LDI at all measured time points as compared to baseline
- Change in LEI at all measured time points as compared to baseline
- Change in FACIT-F at all measured time points as compared to baseline
- Change in BASDAI at all measured time points (in subjects with baseline inflammatory spondylitis, based on investigator judgment, in Study 1311.5) as compared to baseline

5.3.4 Safety Variables

Safety will be assessed descriptively based on:

- Adverse events*
- Serious adverse events (SAEs)
- Clinical laboratory values (hematology, clinical chemistry and urinalysis)
- Physical examination
- Vital signs
- 12-lead ECG
- Local tolerability

* Intensity of adverse events will be assessed by Rheumatology Common Toxicity Criteria (RCTC) version 2.0 developed by OMERACT.¹¹

5.3.5 Pharmacokinetic Variables

Risankizumab plasma concentrations will be determined. PK and ADA data may be combined with data from other studies and analyzed using a mixed-effects modeling approach. This analysis will estimate the population central value and the empirical Bayesian estimates of the individual values for risankizumab apparent clearance (CL/F) and volume of distribution (V_{ss}/F). Additional parameters may be estimated if useful in the interpretation of the data.

5.4 Removal of Subjects from Therapy or Assessment

5.4.1 Discontinuation of Individual Subjects

A subject may withdraw from the study at any time. The Investigator may discontinue any subject's participation for any reason, including an adverse event, safety concerns or failure to comply with this protocol.

Subjects will be withdrawn from the study drug and prematurely discontinued if any of the following occur:

- A subject does not attain a protocol defined response (defined as an improvement in tender and swollen joint count of $\geq 20\%$ compared with the baseline in Study 1311.5) at 2 consecutive visits at Week 12 visit, or thereafter.
- A subject experiences a moderate/grade 2 or above (Rheumatology Common Toxicity Criteria v 2.0) non-serious AE of a systemic hypersensitivity reaction, for which there is no clear alternative explanation.
- A subject experiences a moderate/grade 2 adverse event of vasculitis (Rheumatology Common Toxicity Criteria v 2.0) for which there is no clear alternative explanation.
- Subject experiences severe, grade 3 or greater, or life threatening injection site reaction (ISR) (as defined by the Rheumatology Common Toxicity Criteria v 2.0) which includes prolonged induration, superficial ulceration and includes thrombosis or major ulceration or necrosis requiring surgery.
- A subject has a confirmed platelet count $< 50,000$ cells/mm³ (Rheumatology Common Toxicity Criteria v 2.0).
- Clinically significant confirmed abnormal laboratory results or adverse events, which rule out continuation of the study drug, as determined by the Investigator and the AbbVie study designated physician.
- The Investigator believes it is in the best interest of the subject.
- The subject requests withdrawal from the study, and is no longer willing to participate in study procedures or receive contact from the site.
- Inclusion and exclusion criteria violation was noted after the subject started study drug, when continuation of the study drug would place the subject at risk as determined by the AbbVie study designated physician.
- Introduction of prohibited medications or dosages when continuation of the study drug would place the subject at risk as determined by the AbbVie study designated physician.
- The subject becomes pregnant while on study drug.

- Subject is significantly non-compliant with study procedures which would put the subject at risk for continued participation in the trial in consultation with the AbbVie study designated physician.

If, during the course of study drug administration, the subject prematurely discontinues study participation, the procedures outlined for the early EOT visit must be completed, ideally within 2 weeks of the decision and preferably prior to the initiation of another therapy. However, these procedures should not interfere with the initiation of any new treatments or therapeutic modalities that the Investigator feels are necessary to treat the subject's condition. For subjects that prematurely discontinue, study drug will not be given at the early EOT visit and subjects should attend their EOS Visit 16 weeks after last study drug dose and complete a Follow-up Phone Call 20 weeks after the last dose of study drug to determine the status of any ongoing AEs/SAEs or the occurrence of any new AEs/SAEs (see [Appendix C](#)).

Subjects who prematurely discontinue from study drug will not be required to collect x-rays at a designated time point, unless they received a dose within the 16 weeks prior to the scheduled time point.

All attempts must be made to determine the primary reason for premature discontinuation. The information will be recorded on the appropriate eCRF page.

For subjects that are considered lost to follow-up, reasonable attempts must be made to obtain information on the final status of the subject. At a minimum, two phone calls must be made and one certified letter must be sent and documented in the subject's source documentation.

Subjects who discontinue the study prematurely will not be replaced.

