Administration of study drug will occur at Week 0, 12, 24 and 36, with an additional dose of rizankizumab made available at the Week 4 visit for those subjects that have not achieved a protocol defined response (defined as an improvement in tender and swollen joint count of \geq 20% compared with the baseline in Study 1311.5), provided the investigator believes this may be beneficial to the subject. Subjects who have not attained a protocol defined response at 2 consecutive visits at Week 12 visit or thereafter, will be discontinued from the OLE study. Other criteria leading to discontinuation of individual subjects in this trial are described in Section [5.4.1](#).

A \pm 4-day window is permitted around scheduled study visits after enrollment. If any visit has to be rescheduled, subsequent visits should follow the original visit date schedule.

Follow-Up Period

Subjects will have follow-up visits at Week 48 and 52 and a Follow-up Phone call 20 weeks after the last dose of study drug. All Follow-up Visit procedures are noted in [Appendix C](#). Subjects who discontinue study drug treatment early will need to attend an early End of Treatment (EOT) visit ideally within 2 weeks after the decision and preferably prior to the administration of any new therapies. An End of Study (EOS) visit 16 weeks after the last dose of study drug and a Follow-up Phone Call 20 weeks after the last dose of study drug is required to determine the status of any ongoing AEs/SAEs or the occurrence of any new AEs/SAEs (see [Appendix C](#) and Section [5.4.1](#)).

A schematic of the study design is shown below in [Figure 2](#).

Figure 2. Study M16-244 Study Design

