In the case of a tuberculosis-related adverse event, a supplemental case report form that provides additional information is to be completed by the investigator or designee.

See [Appendix D](#) for TB testing instructions for Japan sites.

Other Safety Parameters

Local Tolerability

Local tolerability at the administration site of the previous subcutaneous injection will be assessed by the investigator according to "swelling," "induration," "heat," "redness,"

"pain," or "other findings" at the specified visits as noted in [Appendix C](#). Any abnormal findings at the injection site during the current visit will be reported as AEs.

Assessments and Patient Reported Outcomes

Clinical and patient reported efficacy endpoints will be assessed over the course of the study at the time points defined in [Appendix C](#). Patient Reported Outcomes (PROs) should be completed by the patient on his/her own in a pre-specified order in a quiet area/room before any other visit assessments or treatments, and, if possible, before any interaction with the investigator or other members of the study team. Details of the following clinical, efficacy and patient reported efficacy assessments are listed in the appendices.

- Tender (68) and Swollen (66) Joint Count
- ACR Response Components
- Dactylitis (LDI)
- Enthesitis (LEI and SPARCC)
- MDA
- DAS28-hsCRP
- EULAR response criteria
- PsARC response
- PASI and sPGA for patients with $\geq 3\%$ BSA of psoriatic plaques at baseline in Study 1311.5 and/or current visit
- mNAPSI
- mTSS

Patient Reported Outcomes

The order of completion should be as follows, applicable for each PRO as specified in [Appendix C](#).

- PtGA

- Patient's Assessment of PsA Pain Intensity (VAS)
- HAQ-DI
- BASDAI – For subjects that presented with inflammatory spondylitis at baseline to Study 1311.5 based on investigator judgment.
- SF-36
- FACIT-F

Study Drug Administration

Refer to Section [5.5.1](#).

Monitoring for Hypersensitivity Reactions

Subjects should be closely monitored for signs and symptoms of hypersensitivity reactions for approximately 2 hours after the first dose administration (baseline visit) and 1 hour after all other dose administrations at study visits. Hypersensitivity reactions should be treated according to medical standards. Pre-medications for further injections might be considered and will be agreed on between investigator and the AbbVie Medical Director.

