6.1.1.2 Serious Adverse Events

If an adverse event meets any of the following criteria, it is to be reported to AbbVie as a serious adverse event (SAE) within 24 hours of the site being made aware of the serious adverse event.

Death of Subject	An event that results in the death of a subject.
Life-Threatening	An event that, in the opinion of the investigator, would have resulted in immediate fatality if medical intervention had not been taken. This does not include an event that would have been fatal if it had occurred in a more severe form.

Hospitalization or Prolongation of Hospitalization	An event that results in an admission to the hospital for any length of time or prolongs the subject's hospital stay. This does not include an emergency room visit or admission to an outpatient facility.
Congenital Anomaly	An anomaly detected at or after birth, or any anomaly that results in fetal loss.
Persistent or Significant Disability/Incapacity	An event that results in a condition that substantially interferes with the activities of daily living of a study subject. Disability is not intended to include experiences of relatively minor medical significance such as headache, nausea, vomiting, diarrhea, influenza, and accidental trauma (e.g., sprained ankle).
Important Medical Event Requiring Medical or Surgical Intervention to Prevent Serious Outcome	An important medical event that may not be immediately life-threatening or result in death or hospitalization, but based on medical judgment may jeopardize the subject and may require medical or surgical intervention to prevent any of the outcomes listed above (i.e., death of subject, life-threatening, hospitalization, prolongation of hospitalization, congenital anomaly, or persistent or significant disability/incapacity). Additionally, any elective or spontaneous abortion or stillbirth is considered an important medical event. Examples of such events include allergic bronchospasm requiring intensive treatment in an emergency room or at home, blood dyscrasias or convulsions that do not result in inpatient hospitalization, or the development of drug dependency or drug abuse.

For serious adverse events with the outcome of death, the date and cause of death will be recorded on the appropriate case report form.

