Appendix S. Rheumatology Common Toxicity Criteria v.2.0 Example

For designation of adverse event terms not shown in the Rheumatology Common Toxicity Criteria v.2.0¹¹ table, the approach described in Row 1 should be used.

Rheumatology Common Toxicity Criteria v2.0
Standardizing Assessment and Reporting of Adverse Effects in Rheumatology Clinical Trials: Enabling Description of Comparative Safety Profiles for Antirheumatic Therapies

Rheumatology Common Toxicity Criteria v2.0			
Standardizing Assessment and Reporting of Adverse Effects in Rheumatology Clinical Trials: Enabling Description of Comparative Safety Profiles for Antirheumatic Therapies			
1 – Mild Asymptomatic, or transient Short duration (< 1 week) No change in life style No medication or OTC			
2 – Moderate Symptomatic Duration (1 – 2 weeks) Alter lifestyle occasionally meds relieve. (May be prescription), Study drug continued	3 – Severe Prolonged symptoms, reversible, major functional impairment Prescription meds/partial relief May be hospitalized < 24 hr Temporary study drug discontinuation, or/and dose reduced	4 – Includes Life-Threatening At risk of death Substantial disability, especially if permanent. Multiple meds Hospitalised > 24 hr Study drug discontinued	
A. Allergic/Immunologic			
A1. Allergic reaction/hypersensitivity (includes drug fever)	Transient rash: drug fever < 38°C; transient, asymptomatic bronchospasm	Generalised urticaria responsive to meds; or drug fever > 38°C, or reversible bronchospasm	Symptomatic bronchospasm requiring meds; symptomatic urticaria persisting with meds, allergy related oedema/angioedema
A2. Autoimmune reaction	Serologic or other evidence of autoimmune reaction, but patient asymptomatic: all organ function normal and no treatment is required (e.g., vitiligo)	Evidence of autoimmune reaction involving a non-essential organ or functions, requiring treatment other than immunosuppressive drugs (e.g., hypothyroidism)	Reversible autoimmune reaction involving function of a major organ or toxicity requiring short term immunosuppressive treatment (e.g., transient colitis or anaemia)
A3. Rhinitis (includes sneezing, nasal stuffiness, post nasal discharge)	Transient, non-prescription meds relieve	Prescription med. required, slow	Corticosteroids or other prescription med. with persistent disabling symptoms such as impaired exercise tolerance

A. Allergic/Immunologic (Continued)

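### Protocol 5.4.1 makes withdrawal compulsory only for non-serious systemic hypersensitivity reactions, so a serious one has no automatic stop

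*Protocol*

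**What the plan says.** Protocol 5.4.1 opens a list under which withdrawal from study drug is compulsory if any entry is met. The second entry covers a Grade 2 or higher (RCTC v2.0) "non-serious AE of a systemic hypersensitivity reaction, for which there is no clear alternative explanation". No other entry names systemic hypersensitivity.

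Two entries further down the same list could catch a serious reaction, and both need a judgement. One covers clinical events and laboratory findings "which rule out continuation of the study drug, as determined by the Investigator and the AbbVie study designated physician". The other is the investigator's view of the subject's best interest.

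Protocol 6.1.1.2 defines what makes an event serious. The criteria include threat to life and "An event that results in an admission to the hospital for any length of time". Its examples of important medical events include "allergic bronchospasm requiring intensive treatment in an emergency room or at home".

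On continued dosing, Protocol 5.3.1.1 (Monitoring for Hypersensitivity Reactions) adds: "Pre-medications for further injections might be considered and will be agreed on between investigator and the AbbVie Medical Director". It does not say which reactions this covers.

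**The concern.** The word non-serious works as a condition of the entry. Read as written, it takes the reactions with the worst consequences out of the automatic stop and keeps less consequential ones in. The sponsor evidently decided that an unexplained Grade 2 systemic reaction should not be left to case-by-case judgement, and the protocol gives no reason for leaving a serious one there.

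Safety and tolerability are the primary objective (Protocol 4.1), so what is at stake is subject protection on repeat exposure. A second consequence concerns oversight. SAP 7.4 counts subjects who met a withdrawal criterion and were not withdrawn. Continued dosing after a serious systemic reaction would not be counted there through the hypersensitivity criterion, because that criterion was never met.

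**Working it through.** The plan states no figure on this point, so the check is a reading of the rule, followed by two counts.

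**1. The criterion as a logical rule.** The entry requires four conditions together: Grade 2 or above, non-serious, systemic, and no clear alternative explanation.

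| Systemic reaction, no alternative explanation | Meets the entry? | Result |
|---|---|---|
| Grade 2, non-serious | Yes | Mandatory withdrawal |
| Grade 3, non-serious | Yes | Mandatory withdrawal |
| Any grade, serious (admitted, life-threatening, or intensively treated bronchospasm) | No | Judgement-based entries only |

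Appendix S, row A1, puts this at Grade 2: "Generalised urticaria responsive to meds; or drug fever > 38°C, or reversible bronchospasm". Such a reaction, if non-serious, forces withdrawal. The same subject admitted to hospital for any length of time has a serious event under 6.1.1.2 and no longer meets the entry.

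**2. Whether another rule fills the gap.**
- Protocol 5.3.1.1, 5.5.1 and Appendix C footnotes l and q: observation after dosing, treatment, PK/ADA and urine sampling, and a supplemental form. No stop.
- Protocol 6.1.1.2 and 6.1.5: reporting to the sponsor within 24 hours. No dosing rule.
- Protocol 6.1.1.3: stopping values for liver tests only.
- Appendix S, Grade 4 column: mentions discontinuation of study drug, but as a severity descriptor, not a withdrawal rule.
- SAP 7.4, 8.0 and 11.2: reporting of deviations, disposition and adverse events. No dosing rule.

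None makes withdrawal automatic after a serious systemic reaction.

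**3. Comparison within the list.** Four entries in 5.4.1 name a specific reaction or laboratory finding: systemic hypersensitivity, vasculitis, injection site reaction and platelet count. Entries limited to non-serious events: 1 of 4. The injection site entry runs the other way and expressly includes life-threatening reactions.

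**4. Doses that a stop could still prevent.** From Protocol 5.1: "Administration of study drug will occur at Week 0, 12, 24 and 36", plus an optional dose at Week 4.

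| Reaction after dose at | Doses remaining |
|---|---|
| Week 0 | 3 (Weeks 12, 24, 36) + 0 or 1 (Week 4) = 3 to 4 |
| Week 4 | 3 |
| Week 12 | 2 |
| Week 24 | 1 |
| Week 36 | 0 |

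**5. Consistency with entry criteria.** Exclusion criterion 10 (Protocol 5.2.2) bars anyone with a history of hypersensitivity to a systemic biologic. A serious reaction to risankizumab would therefore disqualify a candidate at entry, yet once the subject is enrolled it does not automatically bar the next dose.

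**The case against.** The strongest reply is that the entry was meant as a floor: withdraw even when the event is non-serious. The reference to Grade 2 or above supports this. Grade 4 in Appendix S is described by risk of death, substantial disability or a hospital stay over 24 hours, and such events are generally serious under 6.1.1.2. Read as an exclusion, non-serious empties most of the top of the entry's own grade range. That is probably what the sponsor intended. But it is inference, and a site applying the text cannot be expected to make it. Amendment 1 repaired the wording of the preceding entry and left this one unchanged.

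Three further points stand in part:

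- **Seriousness and grade are different axes.** A non-serious Grade 3 reaction does force withdrawal, and a brief admission is serious at any grade. It would be too simple to say that the rule stops mild reactions and spares severe ones. The exact statement is that seriousness removes a reaction from the rule.
- **Serious reactions are not unwatched.** The sponsor hears of them within 24 hours, pre-medication needs the agreement of the sponsor's Medical Director, and a DMC reviews safety. The gap is between automatic and judged withdrawal; unmonitored re-dosing is not shown.
- **The comparison of four entries carries limited weight.** A platelet threshold would not be expected to mention seriousness. The vasculitis entry has its own wording problem: it names Grade 2 without saying that higher grades count.

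The pre-medication sentence is an ambiguity only. It can be read as covering Grade 1, non-systemic or otherwise explained reactions.

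**Conclusion.** The concern holds. As written, an unexplained systemic hypersensitivity reaction of Grade 2 or above triggers mandatory withdrawal if non-serious and does not if serious. Nothing elsewhere in the protocol or SAP supplies the missing rule. The discretionary entries limit the harm but do not replace the rule.

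The size can be given only as exposure per subject: up to four further doses after a Week 0 reaction, falling to none after Week 36. These counts follow from the dosing schedule and say nothing about frequency. The documents give no rate of serious hypersensitivity, so no expected number of subjects is claimed, and no endpoint or estimate is shown to be affected. The conclusion rests on the literal text; if the sponsor meant the floor reading, the same correction is needed to say so. It should be fixed on grounds of subject protection.

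**What to change.** Reword the entry in Protocol 5.4.1 to: *A subject experiences any serious, or moderate/grade 2 or above (Rheumatology Common Toxicity Criteria v 2.0), systemic hypersensitivity reaction for which there is no clear alternative explanation.* At minimum, delete the word non-serious.

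After the pre-medication sentence in 5.3.1.1 add: *This applies only to reactions that do not meet the withdrawal criterion in Section 5.4.1.*

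If the section is reopened, the vasculitis entry could be extended to higher grades at the same time.

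The SAP needs no change, because the deviation category in SAP 7.4 follows whatever the protocol's withdrawal criteria are. The cost is two sentences in a protocol amendment, the ethics approval that Protocol 9.1 requires before changes take effect, and notification of approximately 70 sites. No procedures, visits or subjects are added.

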5.2.3.3 Prohibited Therapy

Use of the following therapies is prohibited from administration of the first dose of study drug in Study 1311.5 throughout the duration of Study M16-244, including any gap between these two studies:

- Investigational products not otherwise described below

- anti-IL-12/23, and anti-IL-17 agents, including ustekinumab and secukinumab
- Cell-depleting therapies including but not limited to anti-CD20 (e.g., rituximab), investigational agents (e.g., CAMPATH, anti-CD4, anti-CD5, anti-CD3, anti-CD19)
- TNF inhibitors
- JAK inhibitor, Apremilast and leflunomide
- Intra-articular injections (including steroids)
- Intramuscular or intravenous corticosteroid treatment
- Topical PsO treatments such as retinoids, Vitamin A analogs, anthralin and steroids except as permitted in Section 5.2.3.2: Concomitant Therapy
- Oral or injectable PsO medications (not biologicals) including retinoids and fumarates, or any other drugs known to possibly benefit PsO
- Photochemotherapy (e.g., PUVA)
- Any drug known to interfere with or to aggravate PsO including but not limited to lithium and interferons
- Phototherapy (e.g., UVA, UVB)
- Low and high potency opioid analgesics (e.g., methadone, hydromorphone, morphine)
- Live or attenuated vaccines

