A4. Serum sickness	Transient, non-prescription meds relieve	Symptomatic, slow response to meds (e.g., oral corticosteroids)	Prolonged; symptoms only partially relieved by meds; parenteral corticosteroids required	Major organ dysfunction, requires long-term high-dose immunosuppressive therapy
A5. Vasculitis	Localised, not requiring treatment; or rapid response to meds; cutaneous	Symptomatic, slow response to meds (e.g., oral corticosteroids)	Generalised, parenteral corticosteroids required or/and short duration hospitalisation	Prolonged, hospitalisation, ischemic changes, amputation
B. Cardiac				
B1. Arrhythmia	Transient, asymptomatic	Transient, but symptomatic or recurrent, responds to meds	Recurrent/persistent; maintenance prescription	Unstable, hospitalisation required, parenteral meds
B2. Cardiac function decreased	Asymptomatic decline in resting ejection fraction by > 10%, but < 20% of baseline value	Asymptomatic decline of testing ejection fraction \geq 20% of baseline value	CHF responsive to treatment	Severe or refractory CHF
B3. Edema	Asymptomatic (e.g., 1 + feet/calves), self-limited, no therapy required	Symptomatic (e.g., 2 + feet/calves), requires therapy	Symptoms limiting function (e.g., 3 + feet/calves, 2 + thighs), partial relief with treatment prolonged	Anasarca, no response to treatment
B4. Hypertension (new onset or worsening)	Asymptomatic, transient increase by > 20 mmHg (diastolic) or to > 150/100 if previously normal, no therapy required	Recurrent or persistent increase > 150/100 or by > 10 mmHg (diastolic), requiring and responding readily to treatment	Symptomatic increase > 150/100, > 20 mmHg, persistent, requiring multi agency therapy, difficult to control	Hypertensive crisis
B5. Hypotension (without underlying diagnosis)	Transient, intermittent, asymptomatic, orthostatic decrease in blood pressure > 20 mmHg	Symptomatic, without interference with function, recurrent or persistent > 20 mmHg decrease, responds to treatment	Syncope or symptomatic, interferes with function, requiring therapy and sustained medical attention, dose adjustment or drug discontinuation	Shock

B. Cardiac (Continued)			
B6. Myocardial ischaemia	Transient chest pain/ECG changes; rapid relief with nitro	Recurring chest pain, transient ECG ST-T changes; treatment relieves	Angina with infarction, no or minimal functional compromise, reduce dose or discontinue study drug

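### The mandatory vasculitis withdrawal rule names Grade 2 only, so unexplained vasculitis first graded 3 or 4 is left to judgement

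*Protocol*

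**What the plan says.** Section 5.4.1 of the protocol introduces a list of circumstances in which withdrawal from study drug is required. Three consecutive entries are tied to a toxicity grade:

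- Systemic hypersensitivity: "A subject experiences a moderate/grade 2 or above (Rheumatology Common Toxicity Criteria v 2.0) non-serious AE of a systemic hypersensitivity reaction".
- Vasculitis: "A subject experiences a moderate/grade 2 adverse event of vasculitis", graded on the same scale and limited to events without a clear alternative explanation.
- Injection site reaction: "Subject experiences severe, grade 3 or greater, or life threatening injection site reaction".

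The scale is RCTC version 2.0, with Grades 1 to 4 (Protocol Section 6.1.2). Row A5 of Appendix S describes Grade 3 vasculitis as "Generalised, parenteral corticosteroids required or/and short duration hospitalisation" and Grade 4 as "Prolonged, hospitalisation, ischemic changes, amputation".

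The same list has general entries. One covers clinically significant laboratory results or adverse events "which rule out continuation of the study drug, as determined by the Investigator and the AbbVie study designated physician". Another rests on the investigator's view of the subject's best interest. A third is "Introduction of prohibited medications or dosages when continuation of the study drug would place the subject at risk", as judged by the sponsor's physician.

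SAP Section 7.4 counts, as a category of protocol deviation, subjects who met a withdrawal criterion and were not withdrawn.

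**The concern.** A stopping rule should be at least as strict for a worse event. Read literally, this one is not: Grade 2 vasculitis obliges withdrawal, while vasculitis with ischaemic damage does not. The purpose of naming specific events in the list is that stopping drug for them should not depend on a case-by-case decision, and for the worst grades of vasculitis that purpose is lost.

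At stake is mainly subject safety, in a study whose primary objective is safety and tolerability. There is also a reporting consequence. A subject kept on drug after Grade 2 vasculitis would count as a deviation under SAP Section 7.4. A subject kept on drug after vasculitis first graded 4 would not count under this criterion.

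**Working it through.** The check is mainly a comparison of texts, since the plan states no figure on this point.

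**Step 1. What the bullet requires, by grade.** For vasculitis without a clear alternative explanation:

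| Grade | Appendix S, row A5 (Grades 1 and 2 summarised) | Withdrawal as written | With *or above* added |
|---|---|---|---|
| 1 | Localised; no treatment or quick response | Not mandatory | Not mandatory |
| 2 | Symptomatic; slow response to medication | Mandatory | Mandatory |
| 3 | "Generalised, parenteral corticosteroids required or/and short duration hospitalisation" | Judgement only | Mandatory |
| 4 | "Prolonged, hospitalisation, ischemic changes, amputation" | Judgement only | Mandatory |

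Three grades lie at or above the evident threshold (2, 3 and 4). One is named and two are omitted.

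**Step 2. Which events fall in the gap.** Protocol Section 6.1.1.1 has worsening of a reported event recorded as a new event. Vasculitis reported at Grade 2 has therefore already met the criterion before it worsens. What remains is unexplained vasculitis whose first recorded grade is 3 or 4. Dosing visits after Week 4 are 12 weeks apart, so such a first report is plausible.

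**Step 3. Whether another rule makes withdrawal mandatory.**

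- The general adverse-event entry applies only to events "which rule out continuation of the study drug, as determined by the Investigator and the AbbVie study designated physician".
- The best-interest entry depends on the investigator's view.
- Grade 3 vasculitis may need parenteral steroids, and Section 5.2.3.3 prohibits "Intramuscular or intravenous corticosteroid treatment". The matching withdrawal entry still requires the sponsor's physician to find that continuing would put the subject at risk.
- The hypersensitivity entry covers non-serious events only. A hospitalised vasculitis is serious under Section 6.1.1.2.
- Serious adverse event reporting within 24 hours (Sections 6.1.1.2 and 6.1.5) informs the sponsor but does not require withdrawal.
- The general Grade 4 heading in Appendix S mentions discontinuation of study drug. That is a grading descriptor in an example appendix. The appendix directs that row to terms not shown in the table, and vasculitis has its own row.

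None of these makes withdrawal mandatory for Grade 3 or 4.

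**Step 4. How often it might arise.** The documents give no vasculitis rate. Let p be the proportion of subjects with unexplained vasculitis first graded 3 or 4, assumed to be between 0.05% and 0.5%. Take N = 180, the enrolment ceiling. Expected subjects = N × p, and P(at least one) = 1 − (1 − p)^N.

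| Assumed p | Expected subjects | P(at least one) |
|---|---|---|
| 0.0005 | 180 × 0.0005 = 0.09 | 1 − 0.9995^180 = 0.086 |
| 0.001 | 180 × 0.001 = 0.18 | 1 − 0.999^180 = 0.165 |
| 0.005 | 180 × 0.005 = 0.90 | 1 − 0.995^180 = 0.594 |

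These are chances that such an event occurs. They are not chances that a subject is then kept on drug.

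**The case against.** The best defence is that this is shorthand whose meaning nobody disputes, and that several controls stand behind it. The general entries also sit under the mandatory heading: once an event is judged to rule out continuation, withdrawal follows. The Grade 2 rule itself needs a judgement about alternative explanations, so the contrast is not between a purely automatic rule and pure discretion. A hospitalised or life-threatening case reaches the sponsor within 24 hours. Section 6.1.1.1 asks sites to make every attempt to contact the sponsor's physician for direction on restarting study drug after prohibited medication. An independent monitoring committee reviews safety data. Regular doses are 12 weeks apart, so there is usually time to decide before the next one. The neighbouring hypersensitivity entry excludes serious events, so this list does not always make the worst event automatic.

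The objection also says that the incidence range has no source, that it uses the enrolment ceiling, and that it includes events after the Week 36 dose, when withdrawal from drug no longer matters. It adds that SAP Section 7.4 does not say how its category is derived, and that the event would still appear in the adverse event tables.

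Most of this stands as a statement about size. The controls lower the chance that a subject is actually re-dosed, the probabilities are illustrative only, and the effect on the deviation count depends on a literal reading. None of it supplies the missing requirement: every control named informs someone or invites a decision, and none obliges withdrawal at Grade 3 or 4.

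**Conclusion.** The concern holds. The vasculitis criterion, as worded, does not cover the two grades worse than the one it names, and nothing else in the protocol makes withdrawal mandatory for them.

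The size is minor. The gap is confined to unexplained vasculitis first graded 3 or 4. A minimum of Grade 2 was very probably meant, and most investigators would stop drug without being told. No efficacy estimate is affected. The range of 0.09 to 0.9 expected subjects rests wholly on the assumed incidence and on full enrolment, and the conclusion does not depend on it. The correction is still worth making, because this is an operative safety rule and the literal text gives the wrong result for the worst cases.

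**What to change.** In Protocol Section 5.4.1, change the grade wording of the vasculitis bullet to *moderate/grade 2 or above* and leave the rest of the bullet as it is. Take only the grade wording from the hypersensitivity entry. Its restriction to non-serious events should not be carried over, since it would exclude hospitalised vasculitis.

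Apply the same threshold, Grade 2 or above, when identifying subjects for the SAP Section 7.4 category of those who met a withdrawal criterion and were not withdrawn. Appendix S needs no change, and neither does Section 5.5.4.

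The cost is two words at the next amendment or in a memo to sites, and one matching line in the deviation specification. No new data are needed.
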